13.7 Publications and Clinical Study Report

13.7.1 Publication of Study Results

Vertex is committed to reporting the design and results of all clinical studies in a complete, accurate, balanced, transparent, and timely manner, consistent with Good Publication Practices.¹⁷ [_ENREF_17](#)

Publication Planning: Vertex staff along with the lead principal investigators, the steering committee, and/or the publication committee will work together to develop a publication plan.

Authorship: Authorship of publications will be determined based on the Recommendations for Conduct, Reporting, Editing, and Publication of Scholarly Work in Medical Journals, which states that authorship should be based on the following 4 criteria¹⁸:

1. Substantial contributions to conception and design, acquisition of data, or analysis and interpretation of data;
2. Drafting of the article or revising it critically for important intellectual content;
3. Final approval of the version to be published; and
4. Agreement to be accountable for all aspects of the work in ensuring that questions related to the accuracy or integrity of any part of the work are appropriately investigated and resolved.

All authors must meet conditions 1, 2, 3, and 4. All persons designated as authors should qualify for authorship, and all those who qualify should be listed. Contributions such as medical writing, enrollment of subjects, acquisition of funding, collection of data, or general supervision of the research group, alone, do not justify authorship.

Contributors: Contributors who meet fewer than all 4 of International Committee of Medical Journal Editors criteria for authorship will not be listed as authors, but their contribution will be acknowledged and specified either as a group (e.g., “study investigators”) or individually (e.g., “served as scientific advisor”).

Publication Review: As required by a separate clinical study agreement, Vertex must have the opportunity to review all publications, including any manuscripts, abstracts, oral/slide presentations, and book chapters regarding this study before submission to congresses or journals for consideration.

13.7.2 Clinical Study Report

A CSR, written in accordance with the ICH E3 Guideline, will be submitted in accordance with local regulations.

Vertex recommends that subjects and sites refer to local guidance regarding travel restrictions. There are no operational changes to the study protocols for subjects who can travel to the study sites for their visits. However, to ensure continued safety of subjects who *cannot* travel to the study sites for their visits (for any reason due to COVID-19), specific alternative measures are being implemented to minimize the risk of exposure to COVID-19 (see table below). As the COVID-19 pandemic evolves, Vertex will continue to assess the need for additional actions to ensure the safety of all involved in these clinical studies.

Addendum Version 3.0 summarizes additional measures taken for these ongoing CF clinical studies (see table below) to ensure continued safety.

Summary of Changes in Ongoing CF Clinical Studies for Subjects Who Cannot Travel to the Study Site

| Protocol Change | Rationale for Change | Study Number |
|--|--|---|
| Addendum Version 3.0, dated 29 July 2020 | | |
| 
Assessments
 
Unscheduled visit(s) will be permissible at the discretion of the investigator(s) or Vertex. The unscheduled visit(s) may be conducted at any time during the study (including after the protocol defined last study visit) in the event assessments specified to be collected at a scheduled visit were not collected due to COVID-19.
 | 
To ensure subject safety and/or to facilitate evaluation of safety and/or efficacy if assessments are not performed per the schedule in the protocol due to COVID-19.
 | 
[REDACTED]
 
[REDACTED]
 
[REDACTED]
 
[REDACTED]
 
VX18-445-110
 
[REDACTED]
 |
| 
Implementaion of measures described in addenda versions 1.0 and 2.0, as applicable.
 | 
To ensure subject safety and/or to facilitate evaluation of safety and/or efficacy while maintaining study integrity and the safety of subjects and site personnel.
 | 
[REDACTED]
 |

Summary of Changes in Ongoing CF Clinical Studies for Subjects Who Cannot Travel to the Study Site

| Protocol Change | Rationale for Change | Study Number |
|---|--|---|
| Addendum Version 2.0, dated 15 May 2020 | | |
| 
Assessments
 
Weight and height/length/stature may be assessed by subjects or their caregivers using medical grade scales and stadiometers, as indicated per protocol and per local regulation. Sites and subjects will receive training and guidance as needed on these devices.
 
Subjects or caregivers will provide these measurements to site personnel by telephone or video call. Investigators will review results and contact subjects for follow-up as needed. All data will continue to be retained in the subject's source files.
 | 
To allow for collection of key data to assess safety and/or efficacy while maintaining study integrity and the safety of subjects and site personnel.
 
Addendum 1 allowed for these assessments to be performed by qualified personnel conducting the in-home visits. Addendum 2 allows for these assessments to be performed by subjects or caregivers.
 | 
[REDACTED]
 
[REDACTED]
 
[REDACTED]
 
[REDACTED]
 
VX18-445-110
 
[REDACTED]
 
[REDACTED]
 
[REDACTED]
 |

[figure not shown]

Summary of Changes in Ongoing CF Clinical Studies for Subjects Who Cannot Travel to the Study Site

| Protocol Change | Protocol Change | Protocol Change |
|---|--|---|
| Addendum Version 1.0, dated 24 April 2020 | | |
| 
Consenting of Subjects ICFs may be provided electronically or by post mail to subjects (and/or caregivers, as indicated per protocol). The subjects and/or caregivers will review the ICF with an appropriately qualified member of the investigator’s team via telephone contact or video call. After this review, subjects and/or caregivers will consent (or assent, if applicable), and/or re-consent verbally and by signing and dating the ICF and returning it to the site via post mail. The signed and dated ICF will then be signed and dated by the investigator.
 
Subjects participating in select studies may have the opportunity to enroll in longterm extension studies. Informed consent (or assent, if applicable), and/or re-consent for subjects (and/or caregivers, as indicated per protocol) may be obtained per the same process described above, as applicable.
 | 
To provide alternative methods of obtaining re-consent or consent, as applicable, while ensuring subject safety.
 | 
[REDACTED]
 
[REDACTED]
 
[REDACTED]
 
[REDACTED]
 |
| 
Study Drug Shipping Study drug may be shipped directly from the site to the subject, as applicable, and if permitted by local regulations; subject protected health information will not be released to Vertex.
 
Reconciliation, return, and destruction of study drug will continue to occur at the clinical site as indicated per protocol and in adherence to local regulations.
 | 
To ensure subjects can continue treatment with study drug without interruption while ensuring their safety.
 
To clarify that despite these alternative measures, reconciliation, return, and destruction of study drug will remain as indicated per protocol.
 | 
[REDACTED]
 
VX18-445-110
 
[REDACTED]
 |
| 
In-home Visits and/or Telephone Contact Study visits may be conducted as in-home visits by qualified personnel as requested by participating sites on a per-subject basis. In addition, all subjects may be contacted by site personnel by telephone or video call, irrespective of in-home visits.
 | 
To provide subjects the opportunity to continue participation in the clinical studies while ensuring their safety by minimizing the risk to COVID-19 exposure through travel.
 | 
[REDACTED]
 
[REDACTED]
 
[REDACTED]
 |

Summary of Changes in Ongoing CF Clinical Studies for Subjects Who Cannot Travel to the Study Site

| Protocol Change | Protocol Change | Protocol Change |
|--|---|---|
| Addendum Version 1.0, dated 24 April 2020 | | |
| 
Safety Assessments and Reporting
 
Safety assessments, as indicated per protocol, may be performed by qualified personnel conducting the in-home visits (e.g., personnel from site or qualified health care agency). These assessments may include the following, as indicated per protocol, and per local regulation:
 
 • vital signs • pulse oximetry • height/length/stature • weight • physical examination (complete or abbreviated) • pregnancy test (serum or urine) • urinalysis • blood draws for safety test panels (chemistry, LFT panel, lipid panel, hematology, coagulation). 
Blood and/or urine samples for safety assessments are analyzed as indicated per protocol for subjects who have in-home visits.
 
Blood and/or urine samples for safety assessments may be collected and analyzed at local laboratories for subjects who do not have in-home visits, but do not complete the assessment at the site.
 
In addition, safety assessments will be evaluated by telephone. These assessments may include the review of the following:
 
 • AEs • signs and symptoms/systems for CF • medications • planned or unplanned hospitalizations for CF • study drug administration • outcomes related to PEX • outcomes related to antibiotic treatment 
Investigators will review results (in-home and telephone) and contact subjects for follow-up as needed.
 
All data will continue to be retained in the subject’s source files.
 
Any clinically significant finding (e.g., AE, SAE, laboratory abnormalities) will continue to be reported as indicated per protocol.
 | 
To assess the safety and tolerability of the CFTR modulator evaluated in the specific clinical study while ensuring subject safety. These safety assessments will continue to provide safety data while minimizing burden to subjects and site personnel.
 
To clarify that despite these alternative measures, all adverse events and serious adverse events should be reported as indicated per protocol.
 | 
[REDACTED]
 
[REDACTED]
 
[REDACTED]
 
[REDACTED]
 
VX18-445-110
 
[REDACTED]
 
[REDACTED]
 
[REDACTED]
 
[REDACTED]
 |

Summary of Changes in Ongoing CF Clinical Studies for Subjects Who Cannot Travel to the Study Site

| Protocol Change | Protocol Change | Protocol Change |
|---|---|--|
| Addendum Version 1.0, dated 24 April 2020 | | |
| 
Efficacy and Other Assessments Efficacy and other assessments, as indicated per protocol, may be performed by qualified personnel conducting the in-home visits. These assessments may include the following, as indicated per protocol, and per local regulation.
 
In-home Spirometry Assessment A spirometry device may be provided to subjects for in-home assessments of lung function as indicated per protocol. Sites and subjects will receive training and guidance as needed.
 
Patient Reported Outcome CFQ-R questionnaires may be provided to subjects (electronically or post mail) to be completed at home as indicated per protocol. Subjects will return these questionnaires to the site via post mail.
 
Other Assessments
 
 • ECGs • sweat chloride • blood samples for CFTR genotype testing, IRT, PK, FSH, inflammatory mediator, biomarkers, and vitamin levels • fecal samples for FE-1, fecal calprotectin, and other markers of intestinal inflammation 
other patient reported outcomes (e.g., TSQM, SF-12)
 | 
To be able to assess safety, treatment effectiveness, and quality of life measures of the CFTR modulator evaluated in the specific clinical study while ensuring subject safety.
 |   VX18-445-110        |

Summary of Changes in Ongoing CF Clinical Studies for Subjects Who Cannot Travel to the Study Site

| Protocol Change | Protocol Change | Protocol Change |
|---|--|---|
| Addendum Version 1.0, dated 24 April 2020 | | |
| 
Remote Monitoring Vertex has implemented remote monitoring visits where applicable, including remote source data verification, as allowed per local regulations. Remote monitoring will focus on collection of safety data, and data supporting primary and key secondary endpoints.
 | 
To allow for review of key data to inform on the safety of subjects receiving treatment.
 
To allow for review of other key data to inform on the objectives of the study while maintaining study integrity and the safety of subjects and site personnel.
 | 
[REDACTED]
 
[REDACTED]
 
[REDACTED]
 
[REDACTED]
 
VX18-445-110
 
[REDACTED]
 
[REDACTED]
 
[REDACTED]
 |

AE: adverse event; CF: cystic fibrosis; CFQ-R: Cystic Fibrosis Questionnaire-Revised; ECG: electrocardiogram; FE-1: fecal elastase-1; FSH: follicle-stimulating hormone; GCP: Good Clinical Practice; ICF: informed consent form; IRT: immunoreactive trypsinogen; LFT: liver function test; PEx: pulmonary exacerbation; PK: pharmacokinetic; SAE: serious adverse event; SF-12: 12-Item Short Form Health Survey; TSQM: Treatment Satisfaction Questionnaire for Medication

2 MODIFICATIONS

2.1 Modifications to the Approved Clinical Study Protocol

Not Applicable.

2.2 Modifications to the Approved Statistical Analysis Plan

This is the 1st version of Statistical Analysis Plan for the interim analysis and final analysis.

2.3 Modifications to the Approved DMC Charter

Not Applicable.

3 INTRODUCTION

VX18-445-110 (Study 110) is a Phase 3, 2-part, open-label extension study of VX18-445-104 (Study 104). For subjects who participate in both Parts A and B, the total study duration is approximately 148 weeks (from the first dose of study drug in this study), including a 96-week Treatment Period in Part A, a 48-week Treatment Period in Part B and a 4-week Safety Follow up Period. The primary objective is to evaluate the long-term safety and tolerability of VX-445 (elexacaftor, ELX)/tezacaftor (TEZ)/ivacaftor (IVA) in subjects with cystic fibrosis (CF) who are heterozygous for the *F508del* mutation and a gating (F/G) or residual function (F/RF) mutation. Safety data will be periodically reviewed by the independent data monitoring committee (DMC).

This SAP (Methods) documents the planned statistical analyses and data presentations of safety and efficacy endpoints for Part A. The SAP will be amended to include Part B prior to Part B DBL. It is based on the most recent approved clinical study protocol (CSP), the most recent approved DMC charter, the most recent approved electronic case report form (eCRF), and the most recent approved eCRF completion guidelines.

Due to the outbreak of COVID-19, to ensure continued safety of subjects who cannot travel to the study sites for their visits (for any reason due to COVID 19), specific alternative measures are being implemented to minimize the risk of exposure to COVID 19. This SAP summarizes the additional statistical analyses that are related to these alternative measures.

The Vertex Biometrics Department will perform the statistical analysis described in this document. SAS (Version 9.4 or higher) will be used to generate all statistical outputs (tables, figures, listings, and datasets). The SAP (Methods) will be finalized and approved prior to IA data lock. Any revisions to the approved SAP will be documented and approved in an amendment to the SAP.

4 STUDY OBJECTIVES

4.1 Primary Objective

To evaluate the long-term safety and tolerability of ELX/TEZ/IVA in subjects with CF who are heterozygous for the *F508del* mutation and a gating (F/G) or residual function (F/RF) mutation.

4.2 Secondary Objectives

- To evaluate the long-term efficacy of ELX/TEZ/IVA
- To evaluate the pharmacodynamics (PD) of ELX/TEZ/IVA

5 STUDY ENDPOINTS

5.1 Primary Endpoint (Parts A and B)

Safety and tolerability of long-term treatment with ELX/TEZ/IVA based on adverse events (AEs), clinical laboratory values, ECGs, vital signs, and pulse oximetry.

5.2 Secondary Endpoints (Part A only)

- Absolute change from baseline in percent predicted forced expiratory volume in 1 second (ppFEV₁)
- Absolute change in sweat chloride (SwCl)
- Absolute change in body mass index (BMI)
- Absolute change in BMI z-score
- Absolute change in body weight
- Absolute change from baseline in Cystic Fibrosis Questionnaire-Revised (CFQ-R) respiratory domain (RD) score

5.3 Exploratory Endpoints (Part A only)

[figure not shown]
- Absolute change in CFQ-R non-respiratory domain scores
- Inflammatory mediators
- Blood biomarkers

6 STUDY DESIGN

6.1 Overall Design

This is a Phase 3, 2-part, multicenter, open-label study (OLS) for subjects who completed the last Treatment Period visit in the parent study (Study 104) and meet eligibility criteria. A schematic of the study design is shown in Figure 6-1.

Figure 6-1 VX18-445-110 Study Design

ELX: elexacaftor; IVA: ivacaftor; TEZ: tezacaftor

Notes: Parent study refers to Study 104. The timing of the Day 1 Visit, relative to the last scheduled visit of the parent study, is detailed in CSP Section 9.1.1. The figure is not drawn to scale.

- ^a Subjects whose Part B Day 1 is on the same day or within 1 calendar day as the Part A Week 96 Visit do NOT have to repeat any Part B Day 1 assessments that were specified to be performed at the Part A Week 96 Visit. Subjects whose Part B Day 1 is more than 1 calendar day after Part A Week 96 Visit must complete all assessments specified for the Part A Week 96 AND Part B Day 1 Visits.

All subjects will receive ELX/TEZ/IVA (TC) at the same dosage as that in the parent study (Study 104). The planned dosages for the Treatment Period are shown in Table 6-1.

Table 6-1 Planned Dosages

ELX Dosage	TEZ Dosage	IVA Dosage
200 mg qd	100 mg qd	150 mg q12h

ELX: elexacaftor; IVA: ivacaftor; q12h: every 12 hours; qd: once daily; TEZ: tezacaftor

All visits will occur within the windows specified. Please refer to Table 3-1 of the CSP for more details about study visits and assessments.

6.2 Sample Size and Power

The primary and secondary objectives of the study are the evaluation of the long-term safety and tolerability, and long-term efficacy of ELX/TEZ/IVA. This is an open-label study that will enroll subjects who complete the last Treatment Period visit in the parent study and meet eligibility criteria. The parent study is a Phase 3 Vertex study investigating ELX/TEZ/IVA (Study 104). Approximately 250 subjects are expected to enroll in this open-label study.

6.3 Randomization

Randomization is not required because all subjects will be treated identically in a single cohort.

6.4 Blinding and Unblinding

Refer to the CSP section 10.7 for details.

7 ANALYSIS SETS

The following analysis sets are defined: Open-label (OL) All Subjects Set for Part A, 104 Full Analysis Set, OL Full Analysis Set for Part A and OL Safety Set for Part A. Unless otherwise specified, all analysis sets defined in this section will be restricted to Part A data only.

7.1 OL All Subjects Set

The **OL All Subjects Set for Part A** is defined as all subjects who were enrolled (defined as subject having data in the clinical database for the OLS) in the OLS. This analysis set will be used for individual subject data listings and disposition summary tables unless otherwise specified.

7.2 104 and OL Full Analysis Set

The **Study 104 Full Analysis Set (104-FAS)** is defined the same as the FAS definition in the SAP of Study 104.

The **OL Full Analysis Set (OL-FAS) for Part A** is defined as all enrolled subjects who have received at least 1 dose of study drug in the open-label study. The OL-FAS for Part A will be used to summarize subject demographics and baseline characteristics and for all efficacy analyses unless otherwise specified.

7.3 OL Safety Set

The **OL Safety Set (OL-SS) for Part A** is defined as all subjects who received at least 1 dose of study drug in the OLS. The OL-SS for Part A will be used for all safety analyses.

8 ANALYSIS PERIOD

8.1 Parent Study Efficacy Period

The definition of this analysis period is the same as in Study 104 and will be used with the parent study efficacy analysis set (104-FAS) to analyze the efficacy data during the parent study.

8.2 Open Label Extension Period

OL Efficacy Period for Part A: The time from the first dose of study drug in the OLS to the last efficacy assessment, which may be collected up to the Week 96 Visit or the earlier of Day 673 and the end of study participation if subject does not have the Week 96 Visit. This analysis period will be used with the OL-FAS for Part A to analyze the efficacy data during the OLS.

OL Safety Period for Part A: The time from the first dose of study drug in the OLS to 28 days after the last dose date of the study drug in the OLS or to the completion date of study participation (defined in CSP Section 9.1.5) in Part A, whichever occurs first. This analysis period will be used with the OL-SS for Part A to analyze the safety data during the OLS.

The **Treatment-emergent (TE) Period for Part A** is same as the OL Safety Period for Part A.

Note: for subjects who depart study 110 to participate in another qualified Vertex study and return in study 110, the above defined analysis period will exclude the time between the last dose before the discontinuation from study 110 and the first dose after re-enter in study 110.

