9.1.2 Safety Follow-up

The Safety Follow-up Visit is scheduled to occur 28 (\pm 7) days after the last dose of study drug. The Safety Follow-up Visit assessments are listed in [Table 3-1](#).

The Safety Follow-up Visit is required for all subjects. However, subjects who transition within 28 days of the last dose of study drug to either a commercially available or managed access program-supplied next-generation corrector TC regimen, or to another qualified Vertex study, will complete the Week 96 Visit (or the Early Termination of Treatment [ETT] Visit, if the transition occurs before the Week 96 Visit). In these cases, the Week 96 Visit (or the ETT Visit) will replace the Safety Follow-up Visit.

For subjects who complete an ETT Visit 3 weeks or later following the last dose of study drug, the ETT Visit will replace the Safety Follow-up Visit ([Section 9.1.3](#)).

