9.1.5 Completion of Study Participation

Completion of study participation for each individual subject is defined as: the Safety Follow-up Visit; or, in situations in which the ETT Visit or the Week 96 Visit replace the Safety Follow-up Visit (Section 9.1.2), the ETT Visit or the Week 96 Visit.

If subjects withdraw consent or assent, completion of study participation is defined as date of withdrawal of consent or assent, whichever is earlier (Section 9.9).

If subjects are lost to follow-up (Section 9.1.4), the date of completion of study participation will be defined as the date of last contact.

The end of study is defined in Section 13.2.8.

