9.2.5 Study Drug Exposure

Duration of study drug exposure (in days) will be calculated as: last dose date of study drug in the OLS – first dose date of study drug in the OLS + 1, regardless of study drug interruption. For subjects who enroll in another qualified Vertex study before completing this study and resume participation in this study, time spent in the other study will be excluded.

Study drug exposure (in weeks) during OL safety period for Part A for the OL-SS for Part A will be summarized descriptively by the number of subjects (n), mean, SD, median, min, and max. It will also be summarized into the following categories: ≤ 24 weeks, >24 to ≤ 48 weeks, >48 to ≤ 72 weeks, >72 to ≤ 96 weeks, >96 weeks. Additionally, the total study drug exposure, defined as the sum total of the study drug exposure across all subjects (in patient-weeks and patient-years), will be provided. The summary will be presented by treatment group in parent study and overall.

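### For subjects who leave for another Vertex study and return, SAP 8.2 drops the post-dose tail of the safety period that permanent leavers keep

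*SAP*

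**What the plan says.** **General rule.** SAP 8.2 runs the OL Safety Period for Part A from the first open-label dose "to 28 days after the last dose date of the study drug in the OLS or to the completion date of study participation", whichever is earlier. The TE Period "is same as the OL Safety Period for Part A". The OL Efficacy Period is "The time from the first dose of study drug in the OLS to the last efficacy assessment", so neither period stops at the last dose.

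**Rule for returners.** The Note closing SAP 8.2 covers subjects who go to another qualified Vertex study and come back. For them the period is to "exclude the time between the last dose before the discontinuation from study 110 and the first dose after re-enter" Study 110. No post-dose tail is kept.

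**Departure visit.** Protocol 9.1.2 covers subjects who move within 28 days of the last dose to commercial or managed-access treatment "or to another qualified Vertex study, will complete the Week 96 Visit (or the Early Termination of Treatment [ETT] Visit" if they leave before Week 96). It adds: "In these cases, the Week 96 Visit (or the ETT Visit) will replace the Safety Follow-up Visit". Protocol 9.1.5 makes that visit the completion of participation "in situations in which the ETT Visit or the Week 96 Visit replace the Safety Follow-up Visit".

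**Exposure.** For returners, SAP 9.2.5 says that "time spent in the other study will be excluded", and SAP 9.2.6 says the same for compliance. As worded, this is a different interval from the one in the 8.2 Note.

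**The concern.** Whether a finding made shortly after the last dose is treatment-emergent should not depend on whether the subject later comes back. Under the Note it can. All safety analyses use the TE Period (SAP 9.4), including the TEAE tables, the laboratory and ECG threshold tables, and the special-interest summaries of rash and elevated transaminases (SAP 9.5.1). A transaminase rise found at a departure visit after the last dose would enter the threshold table for a permanent leaver and be missing from it for a returner.

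SAP 9.4.1 does not close the gap. Its returner rule flags as pre-treatment only those AEs that began during the other study and are ongoing at the Returning Visit. An AE that begins after the last Study 110 dose but before entry to the other study has no clear category.

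The two exclusion rules also differ. Off-drug days on either side of the other study can count as exposure under 9.2.5 while lying outside the TE Period under 8.2.

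**Working it through.** The plan gives no figure on this point to reproduce. The check applies the two rules to the same subject.

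**1. TE time after the last dose.** Let g be the days from the last Study 110 dose to the departure ETT Visit, and take that visit as completion of participation (Protocol 9.1.2 and 9.1.5).

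- Permanent leaver, general rule: TE days after last dose = min(28, g).
- Returner, 8.2 Note: TE days after last dose = 0.

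| g (days) | Permanent leaver | Returner |
|---|---|---|
| 0 | 0 | 0 |
| 1 | 1 | 0 |
| 7 | 7 | 0 |
| 14 | 14 | 0 |
| 28 | 28 | 0 |
| 35 | 28 | 0 |

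The difference is the interval from last dose to departure visit, capped at 28 days. Protocol 9.1.3 asks for the ETT Visit as soon as possible after the decision to stop, so g is usually above zero and need not be long. Even g = 1 puts the whole visit in the excluded interval. If the visit's assessments precede a final dose on the same day, as Protocol 9.6.1 arranges for scheduled visits, nothing is lost.

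**2. What the visit contains.** Table 3-1 schedules ECG, vital signs, pulse oximetry, hematology, coagulation, serum chemistry, spirometry, sweat chloride and CFQ-R at the ETT Visit. The Note follows the definitions of both the efficacy and the safety period, so on its natural reading the efficacy assessments are excluded too.

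**3. What is not lost.** SAP 9.4.1 lists all AEs whatever their TE status, and lists SAEs and deaths with a TEAE flag. AEs that are new or worse after re-dosing are TEAEs.

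**4. Exposure.** Let D1 and D2 be the two dosing segments, S the time in the other study, and u and w the off-drug days before and after it. Under 9.2.5, read literally:

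exposure = (D1 + u + S + w + D2) − S = D1 + D2 + u + w.

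With assumed D1 = 200, D2 = 300 and S = 60 (500 dosing days):

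| u, w | Exposure (days) | Off-drug days outside the TE Period |
|---|---|---|
| 1, 1 | 502 | 2 (2/502 = 0.4%) |
| 14, 7 | 521 | 21 (21/521 = 4.0%) |
| 28, 28 | 556 | 56 (56/556 = 10.1%) |

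**5. Trial-wide illustration.** The documents give neither the number of returners nor the gap lengths. Assume 5% to 20% of the 250 expected subjects return (about 12 to 50) and u + w is 28 to 56 days, against 96 × 7 = 672 days of treatment. Excess person-time is then 0.05 × 28/672 = 0.2% up to 0.20 × 56/672 = 1.7%. This range concerns exposure only. It does not measure the missing departure-visit findings, for which there is no basis for a figure.

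**The case against.** The strongest objection is that the SAP follows a later protocol than the one supplied. The SAP has a Part B and a Returning Visit; the supplied protocol has neither, and its section 9.1.2 does not address temporary absence. The later version may set out departure and return assessments differently. This stands: that a returner has an off-drug ETT Visit is an inference. It does not change the Note, which keeps no post-dose time for returners wherever the visit falls.

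A reader might infer more than the documents support:

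- **That the period closes at departure.** It is interrupted, and resumes at the first dose after re-entry.
- **That all later AEs disappear.** Only AEs with onset or worsening in the gap leave the TE summaries.
- **That each returner loses 28 days of AE capture.** A transferring permanent leaver's TE Period also ends at the ETT Visit. The loss relative to that subject reaches 28 days only if the visit is that late.
- **That exposure-adjusted rates are shown to be too low.** SAP 9.4.1 plans such rates without naming the denominator, and the time spent in the other study could be read as the whole absence, which would agree with 8.2. The dilution is conditional on a literal reading of 9.2.5 and on its use as the denominator.

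It is also fair to say that off-drug efficacy data may reasonably be left out, and that 9.2.5 counts interruption days as exposure for everyone. During an ordinary interruption, however, the TE Period normally continues and AEs count; in the returner gap they do not.

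**Conclusion.** The inconsistency is real and follows from a stated rule. For returners only, SAP 8.2 removes the post-dose tail that its general definition keeps, and no other section restores it. The consequence for TEAE and threshold summaries rests on two assumptions: that the departure visit is the ETT Visit of Protocol 9.1.2, and that it follows the last dose. The unequal interval is min(28, g) days per returner. The total effect cannot be computed from the documents and is probably small, because only returners are affected and the visit is meant to be prompt. The exposure mismatch is a second, conditional point. Because the rule touches the primary safety endpoint and costs little to correct, it should be changed.

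**What to change.** - **SAP 8.2:** end a returner's first segment at the earliest of (a) the departure visit that replaced the Safety Follow-up Visit, (b) 28 days after the last Study 110 dose before departure, and (c) the first dose in the other study. Restart at the first dose after re-entry. State that this applies to both the efficacy and the safety period.
- **SAP 9.4.1:** classify AEs that start or worsen in that tail as TEAEs.
- **SAP 9.2.5 and 9.2.6:** compute exposure as the sum of the Study 110 dosing segments, each as last dose minus first dose plus 1. This matches how exposure is defined for non-returners and keeps off-drug days around the other study out of it. It does not make exposure equal to the TE Period, which includes a post-dose tail for everyone.

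The cost is a few sentences and a small programming change, with no new data. Reported event counts may rise slightly.
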